8.2 Secondary Endpoints

All subjects will be considered to be evaluable for the secondary endpoints.

1. The frequency, nature, causality and severity of adverse events.
2. The occurrence of variations in biochemical parameters which would indicate renal or hepatic impairment.
3. Evidence for seroconversion to HIV-1/HIV-2, HAV, HBV, HCV and parvovirus B19 for subjects who are seronegative for these viruses upon enrollment.
4. The amount of product used per year as part of at-home prophylaxis and therapy for bleeding episodes.
5. A physician's qualitative assessment of hemostasis (evaluated as "None," "Moderate," "Good," or "Excellent") in response to therapy with Alphanate[®] received by the subject in a hospital or at another location under the physician's direct supervision.

With this section, the design of this clinical trial satisfies the recommendations of the CPMP for trials in previously-treated patients of concentrates with marketing authorization in which a manufacturing process has been added.

9 STATISTICAL PLAN

9.1 Sample Size

The sample size of 50 to 80 evaluable patients followed for at least two years for renal or hepatic function and evidence of seroconversion to HIV-1/HIV-2, HAV, HBV, HCV and parvovirus B19 is in accordance with the recommendations of the CPMP regarding post-authorization surveillance of previously-treated patients infused with a coagulation factor concentrate:

- for which a marketing authorization has already been granted and
- in the production of which a manufacturing process has been added.

9.2 Planned Method of Analysis

9.2.1 Primary Endpoint

Incidence of Antibody Inhibitors to Factor VIII in Individuals Treated with Alphanate[®]

Assuming a maximum biannual rate of inhibitor incidence of three percent in multi-transfused hemophilia patients, the 95% one-sided confidence interval for this incidence rate in a sample of 50 subjects is up to two percent. Thus,

Contains Confidential and Proprietary Information of Grifols Inc.

with a sample of 50 evaluable subjects monitored for two years, if one subject develops an antibody inhibitor to Factor VIII with a titer higher than 0.6 modified BU/mL, that persists for at least one month, the incidence of inhibitors to Factor VIII will be judged to be higher than that for patients with hemophilia A who are treated with currently marketed Factor VIII concentrates. If the sample size is increased to 80 subjects, no more than 1 subject may develop an antibody inhibitor to Factor VIII.

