7.8 Miscellaneous

All enrollment tests should be performed prior to the first administration of Alphanate®. Samples drawn for quarterly testing will be drawn \pm 10 days of the scheduled visit date. The presence of inhibitors will be determined by the Nijmegen modification of the Bethesda assay (see below); the Factor VIII source for this assay will be normal pooled plasma. **Inhibitor titers will be considered valid if the subject's Factor VIII level is at or below baseline (less than 0.01 IU/mL)**, therefore, the subject should be scheduled for the quarterly visit at least three days after an infusion with Alphanate®.

If the subject's Factor VIII levels are higher than baseline at the time the plasma sample is drawn, then the subject will be rescheduled for testing within one week of the notification of the invalid result.

Assays for inhibitor to Factor VIII will be performed locally (i.e., at the coagulation testing laboratory for each clinical site) to support decisions regarding treatment. Duplicate plasma samples will be collected at each time point for confirmatory testing at a central reference laboratory. The central laboratory will utilize the Nijmegen modification of the Bethesda assay to improve reliability.¹⁷ The modification involves the following changes in reagents: (1) buffering of the normal pooled plasma used in the assay and control with 0.1 M imidazole to pH 7.4 and (2) replacing the imidazole buffer in the control mixture with immunodepleted Factor VIII-deficient plasma. In addition, to further improve the accuracy of the assays, a standardized immunodepleted plasma will be used for the performance of the assay at all clinical sites, as well as at the central reference laboratory.

The local laboratories will not be required to test for Factor VIII inhibitors using the Nijmegen modification of the Bethesda assay, but are required to provide the sponsor with a detailed description of the procedure used.

Contains Confidential and Proprietary Information of Grifols Inc.

Only the results of the assays from the central reference laboratory will be used in the determination and analysis of the primary endpoint for the clinical trial.

To determine the risk of transmission of parvovirus B19, subjects who are seronegative at enrollment will be tested approximately one week after receiving the first infusion with Alphanate[®] for the presence of parvovirus B19 by Polymerase Chain Reaction (PCR) testing.

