8.1 Primary Endpoint

Incidence of antibody inhibitors to Factor VIII in at least 50 evaluable subjects will be determined following a period of at least two years and a minimum of 50 exposure days or if 50 exposure days are not reached, a maximum of 30 months. Only one exposure-day will be accrued for each surgical episode independent of the number of days of treatment or the number of infusions. For the purpose of this endpoint only, a subject is determined to be evaluable when his clinical experience after the date of enrollment includes at least 50 CEDs of treatment with Alphanate[®] or when he develops inhibitors with a titer greater than or equal to 5 BU/mL as determined by the central reference laboratory.

Contains Confidential and Proprietary Information of Grifols Inc.

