4. SAMPLE SIZE CONSIDERATIONS

Assuming a maximum biannual rate of inhibitor incidence of three percent in multi-transfused hemophilia patients, the 95% one-sided confidence interval for this incidence rate in a sample of 50 subjects is up to two percent. Thus, with a sample of 50 evaluable subjects monitored for two years, if one subject develops an antibody inhibitor to Factor VIII with a titer higher than 0.6 modified BU/mL, that persists for at least one month, the incidence of inhibitors to Factor VIII will be judged to be higher than that for patients with hemophilia A who are treated with currently marketed Factor VIII concentrates. If the sample size is increased to 80 subjects, no more than 1 subject may develop an antibody inhibitor to Factor VIII.

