5. ANALYSIS POPULATIONS

5.1 Safety Population

The safety analysis population consists of all patients who were randomized and received at least one Alphanate® treatment; no treated patients will be excluded from the safety analysis population.

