6.5 Significance Level

Unless otherwise noted, all statistical analyses will be conducted with a significance level (α) of 0.05 and utilize two-sided testing.

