9. STATISTICAL ANALYSIS

9.1 Primary Analysis

Analysis of the primary safety endpoint will be conducted on the Safety Population. The primary safety endpoint, presence/absence of Factor VIII inhibitors, will be summarized with frequencies and percentages.

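### The two percent confidence limit for 50 subjects is wrong (exact one-sided 95% upper limits are 5.8% with no case and 9.1% with one), and one case in 50 cannot support a conclusion of higher inhibitor incidence

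*Protocol*

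**What the plan says.** Protocol 9.2.1 takes 3% as the maximum *biannual* inhibitor rate in multi-transfused patients and says that "the 95% one-sided confidence interval for this incidence rate in a sample of 50 subjects is up to two percent". SAP 4 repeats this. Both then draw a rule from it. If one of 50 evaluable subjects followed for two years has a titer above 0.6 modified BU/mL lasting at least a month, "the incidence of inhibitors to Factor VIII will be judged to be higher than that for patients with hemophilia A" on marketed concentrates. For the larger sample: "If the sample size is increased to 80 subjects, no more than 1 subject may develop an antibody inhibitor to Factor VIII".

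The analysis section of the SAP is narrower. SAP 9.1 says: "The primary safety endpoint, presence/absence of Factor VIII inhibitors, will be summarized with frequencies and percentages". It uses the Safety Population, from which, under SAP 5.1, "no treated patients will be excluded from the safety analysis population". The rule is instead written for evaluable subjects. Under Protocol 8.1, "a subject is determined to be evaluable when his clinical experience after the date of enrollment includes at least 50 CEDs" on the product, or when he reaches a central-laboratory titer of 5 BU/mL or more. Protocol 7.8 adds: "Only the results of the assays from the central reference laboratory will be used in the determination and analysis of the primary endpoint".

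**The concern.** An upper limit of 2% cannot surround an assumed rate of 3%, and 50 subjects are too few to exclude rates above 2% even if no inhibitor appears. The figure therefore overstates the reassurance that the trial can give.

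The rule built on it errs in the other direction. One case in 50 is an observed 2.0%, which is below the assumed 3% and within the stated limit, yet it would lead to a conclusion of excess incidence. This is the only comparative conclusion written for the primary endpoint. If it were carried into a report as worded, a product no more immunogenic than its comparators could readily be described as worse.

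**Working it through.** **Inputs.** n = 50 or 80, reference rate 3%, one-sided 95% (Protocol 9.2.1, SAP 4). *Biannual* is read as once in two years, which fits the two-year monitoring in the same paragraph. Two other rates come from the Protocol Introduction:
- 8 per 1,000 patient-years, so 2 × 0.008 = 1.6% over two years. That cohort includes non-severe patients.
- 1/86 = 1.2%, for which no time base is given.

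Neither is used in 9.2.1.

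**Trying to reproduce 2% for n = 50.**
- Wilson upper limit: 5.1% (0 cases), 8.5% (1 case).
- Wald around 3%: 0.03 + 1.645 × √(0.03 × 0.97/50) = 7.0%. Wald around 1/50: 5.3%.
- Exact Poisson over 100 patient-years: 3.0% per year (0 cases), 4.7% per year (1 case).

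Two routes do give 2%, but neither is a confidence limit for 50 subjects. One is the observed proportion 1/50. The other is the half-width 1.645 × √(0.015 × 0.985/100) = 2.0%, whose upper limit would be 3.5% per year.

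**Exact limits (Clopper-Pearson, one-sided 95%).** For 0 cases the upper limit is 1 − 0.05^(1/n), which for n = 50 is 5.8%. For x cases it is the p that solves P(X ≤ x | n, p) = 0.05.

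| Cases | Upper limit, n = 50 | Upper limit, n = 80 |
|---|---|---|
| 0 | 5.8% | 3.7% |
| 1 | 9.1% | 5.8% |
| 2 | 12.1% | 7.7% |

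A 2% upper limit with no case needs ln(0.05)/ln(0.98) = 148.3, so 149 subjects.

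**What one case shows.** The lower limit for 1/50 is 1 − 0.95^(1/50) = 0.10%. The one-case rule is thus a 5% test only against a true rate of about 0.10%. The lower limit for 2/80 is 0.45%.

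**How often the rules fire.** For n = 50: P(X ≥ 1) = 1 − (1 − p)^50. For n = 80, reading the sentence as the same rule with two or more cases: P(X ≥ 2) = 1 − (1 − p)^80 − 80p(1 − p)^79.

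| True two-year rate | 1 or more in 50 | 2 or more in 80 |
|---|---|---|
| 3% (the plan's maximum) | 78.2% | 69.6% |
| 1.6% | 55.4% | 36.7% |
| 1/86 | 44.3% | 23.8% |

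**Sensitivity for n = 50.** If only half of the cases behind the 3% or 1.6% met the titer and persistence criteria (an assumption), the rule fires 53.0% or 33.1% of the time. If *biannual* meant twice a year at constant risk, the two-year rate would be 1 − 0.97^4 = 11.5% and the rule would fire 99.8% of the time.

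**The case against.** The strongest reply is that little hangs on the sentence. The SAP places it under sample size, calls its analysis primarily descriptive (6.4) and plans only counts and percentages (9.1). No planned table applies the rule, no study action follows from it, and Protocol 9.1 rests the 50 to 80 subjects on the CPMP recommendation. A low alarm threshold can also be defended in a safety study. All of this stands, and it limits the weight of the point. It does not make the limit right. Protocol 9.2.1 sits under the planned method of analysis, and nothing elsewhere withdraws the conclusion.

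Three stronger readings are tempting, but the documents do not support them.
- A reader might infer that the trial will mislabel the product about four times in five. The 78% applies at a rate that the plan calls a maximum, and no rate for marketed concentrates is stated, so the size depends on an unnamed comparator.
- A reader might infer that the sample size must change. It was not derived from this limit.
- A reader might replace one case with a corrected count now, such as 5 in 50, because P(X ≥ 5 | 50, 3%) = 1.7%. That is premature. Protocol 8.1 makes evaluability depend partly on outcome. Suppose that every case were counted but 20% of event-free subjects were non-evaluable (an assumption). A true 3% would then appear as 0.03/(0.03 + 0.97 × 0.8) = 3.7%, and a true 1.6% as 2.0%. A 5-in-66 threshold against 3% would move from 4.8% to 9.9% false positives, and a 3-in-50 threshold against 1.6% from 4.6% to 7.8%. Follow-up of up to 30 months also does not match a two-year benchmark: if every subject were followed that long, 1.6% becomes 2.5 × 0.008 = 2.0%, and 3-in-50 again has about 7.8%.

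**Conclusion.** The concern holds for the stated limit and for the conclusion drawn from it. With 50 subjects the one-sided 95% upper limit is 5.8% at best, nearly three times the stated figure. One case gives a lower limit of 0.10% and cannot show an incidence above any reference rate in the documents. The one-case rule fires 44% to 78% of the time across those rates, and the 80-subject version 24% to 70%. These figures assume independent subjects with complete follow-up, *biannual* read as two-yearly, and reference rates that count the same kind of case as the rule. Halving the qualifying cases still leaves 33% to 53% for n = 50. The defect therefore survives these readings, although its size does not stay fixed at 78%. It is an important correction to the wording and the primary summary, and not a change to the design.

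**What to change.** Keep 50 to 80 evaluable subjects.

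(a) In Protocol 9.2.1 and SAP 4, replace the two percent figure with the exact limits tabulated above. Write *two-year* for *biannual* if that is meant.

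(b) Withdraw the conclusion of higher incidence as the consequence of one case in 50. One in 50 and two in 80 may stay as review signals, with their false-signal rates stated. Conclude that incidence is higher only if the exact one-sided 95% lower limit exceeds a benchmark that is named with its source before data review and matched to the trial's population and follow-up time. Set case-count thresholds only once the benchmark, analysis set and time base are fixed.

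(c) In SAP 9.1, add exact one-sided 95% limits to the Safety Population frequency, where no treated subject is dropped because of outcome. State this as an exception to SAP 6.5, which sets a level "of 0.05 and utilize two-sided testing". Show evaluable subjects (Protocol 8.1) as a second summary.

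(d) Reconcile the inhibitor definitions. Protocol 7.11 uses 0.6 modified BU/mL or greater, 9.2.1 uses above 0.6 with one month's persistence, and 8.1 uses 5 BU/mL or more. As written, a confirmed high-titer subject who is withdrawn before one month could be evaluable and yet count as a non-case. The definition should prevent that.

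**Cost.** Wording in two documents and one added interval, with no new patients. Protocol 13.1 requires the amendment to be reviewed and approved before use. The stated precision becomes less favourable, and power to conclude that incidence is higher is limited. As an illustration, 5 in 50 against 3% would detect a true 6% only 18% of the time, and 6 in 80 only 35%. That is a reason to keep the low counts as review signals.

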1 INTRODUCTION

The development of an immune response to Factor VIII (*i.e.*, the generation of antibody inhibitors of Factor VIII) by patients diagnosed with hemophilia A and treated with Factor VIII concentrates is a serious complication in the treatment of hemophilia A.^{1,2} Estimates of inhibitor formation from retrospective and prospective clinical trials vary from as low as four percent to as high as 28 percent. All studies agree that prevalence of antibody inhibitors is higher among individuals with severe hemophilia A (Factor VIII:C less than 0.01 IU/mL) than among individuals with mild or moderate disease, with estimates ranging from eight to 28 percent.^{3,4}

In clinical trials in which previously-untreated or minimally-treated patients (PUPs) were treated with recombinant Factor VIII concentrates, the incidence of inhibitors to Factor VIII was measured as a function of cumulative exposure days (CEDs). In a clinical trial conducted by Bray *et al.*⁵, inhibitors developed in 17 of 71 (24%) PUPs treated with Recombinate® (Baxter Bioscience); 5 of the 71 (7%) patients developed high-responder inhibitors. The median number of CEDs was 11 for all patients and nine for patients who developed inhibitors.

Similarly, in a clinical trial conducted by Lusher *et al.* of subjects receiving Kogenate® (Bayer), inhibitor formation occurred in 16 of 62 (27%) subjects.⁶ Seven of the 62 (11%) patients developed high-responder inhibitors. The median number of CEDs was nine for patients who developed inhibitors and 28 for subjects who exhibited no immune response to Kogenate®.

Several clinical trials have been conducted in which PUPs were enrolled and then treated with plasma-derived Factor VIII concentrates of varying purity and produced using differing virucidal treatments (*e.g.*, terminal dry heat, pasteurization, solvent-detergent).⁷⁻⁹ The rates of incidence for antibody inhibitors ranged from 21 to 28 percent, a range similar to that observed with recombinant Factor VIII products. Consequently, the investigators for these trials concluded that recombinant DNA products do not pose any greater risk for inhibitor formation in PUPs than do plasma-derived products.

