A study of the incidence of inhibitors in previously-treated patients (PTPs) carried out by McMillan *et al.* included 1306 hemophilia patients whose mean age was 18, and who were followed for up to four years. Thirty-one of these individuals (2.4 percent) developed inhibitors to Factor VIII; of these, 29 had been diagnosed with severe hemophilia A. The incidence of new inhibitors was eight per 1,000 patient-years of observation.

In a study of PTPs treated with recombinant Factor VIII (Kogenate®), by Schwartz *et al.*, inhibitor formation was observed in only 1 of 86 (1.2%) patients following repeated exposure to the product.¹⁶ The mean annual per capita consumption of Factor VIII in this subgroup was estimated to be approximately 78,000 units annually.

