3 OBJECTIVE

The objective of this study is to determine the immunologic and overall safety associated with long-term use of Alphanate® in individuals diagnosed with severe hemophilia A (Factor VIII:C less than 0.01 IU/mL), who have been previously treated with plasma-derived Factor VIII products other than Alphanate® and who have no history of developing either antibody inhibitors to Factor VIII or nonspecific inhibitors of coagulation.

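### The inhibitor rule is benchmarked on multi-transfused patients at 3% but words its verdict against hemophilia A patients generally, and one case in 50 does not support "higher" even against the matched 3%

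*Protocol*

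**What the plan says.** Protocol 9.2.1 opens with the benchmark: "Assuming a maximum biannual rate of inhibitor incidence of three percent in multi-transfused hemophilia patients". It adds that "the 95% one-sided confidence interval for this incidence rate in a sample of 50 subjects is up to two percent", and draws the decision rule from this: "with a sample of 50 evaluable subjects monitored for two years, if one subject develops an antibody inhibitor" above 0.6 modified BU/mL that lasts at least a month, the incidence "will be judged to be higher than that for patients with hemophilia A who are treated with currently marketed Factor VIII concentrates". For a larger trial it says: "If the sample size is increased to 80 subjects, no more than 1 subject may develop an antibody inhibitor to Factor VIII". SAP 4 repeats the paragraph.

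The enrolled population is narrower than the one in the verdict. Protocol 3 limits the objective to severe disease in patients "who have been previously treated with plasma-derived Factor VIII products other than Alphanate® and who have no history of developing either antibody inhibitors". Protocol 5.1 requires at least 150 cumulative exposure days and excludes anyone ever diagnosed with an inhibitor.

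There is no concurrent control (Protocol Summary; SAP 2.2). SAP 9.1 plans only frequencies and percentages for the primary endpoint, with no interval and no reference rate.

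**The concern.** With no control arm, the external population named in the rule is the only comparator. Within one paragraph it goes from multi-transfused patients to patients with hemophilia A on marketed concentrates, with no limit on prior treatment, severity or inhibitor history. A report that reproduced the verdict sentence would make a claim about a population that the trial neither enrols nor benchmarks.

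The threshold is the larger fault. One case in 50 is an observed 2%, under the 3% the rule takes as its ceiling, yet it is to be called higher. The primary conclusion could therefore count against the product on data that show no excess over the stated benchmark.

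**Working it through.** **Inputs**
- Benchmark 3%, multi-transfused patients (Protocol 9.2.1, SAP 4). I read *biannual* as per two years, because the rule follows subjects for two years.
- Rules: at least 1 of 50, or at least 2 of 80 (same sections).
- Previously treated cohort in Protocol 1: "The incidence of new inhibitors was eight per 1,000 patient-years of observation". Over two years, 1 − exp(−2 × 0.008) = 1.59%, taken as 1.6%.
- Other previously treated figures in Protocol 1: 31 of 1,306 (2.4%) over up to four years, and 1 of 86 (1.2%).

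**Step 1: the plan's own figure.** I cannot reproduce the one-sided 95% limit of 2% at n=50.
- 0 of 50, exact upper limit: 1 − 0.05^(1/50) = 5.8%.
- 1 of 50, exact upper limit: 9.1%.
- Normal approximation around 3%: 0.03 + 1.645 × √(0.03 × 0.97/50) = 7.0%.

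The only 2% available is the point estimate, 1/50.

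**Step 2: what one case shows.** The exact one-sided 95% lower limit for 1 of 50 is 1 − 0.95^(1/50) = 0.10%. One case is evidence of an excess only over a reference rate of about 0.1% or less.

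**Step 3: how often the rule says higher when the true rate equals the reference.**
- P(at least 1 of 50) = 1 − (1 − p)^50
- P(at least 2 of 80) = 1 − (1 − p)^80 − 80p(1 − p)^79

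| True two-year rate | At least 1 of 50 | At least 2 of 80 |
|---|---|---|
| 3% | 1 − 0.218 = 78% | 1 − 0.087 − 0.216 = 70% |
| 1.6% | 1 − 0.446 = 55% | 1 − 0.275 − 0.358 = 37% |

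These probabilities depend only on the product's true rate. Renaming the comparator does not change them.

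**Step 4: counts that would support the verdict.** Take the smallest count whose exact upper tail probability at the reference rate is at most 5%; equivalently, the exact one-sided 95% lower limit lies above the reference.

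| Reference | n=50 | Tail (one fewer case) | n=80 | Tail (one fewer case) |
|---|---|---|---|---|
| 3% | 5 cases | 1.7% (6.3%) | 6 cases | 3.3% (9.3%) |
| 1.6% | 3 cases | 4.6% (19.1%) | 4 cases | 4.0% (13.7%) |

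**Step 5: sensitivity at those counts, n=50.** Protocol 1 reports a 4.5-fold increase for one pasteurized concentrate. I add a doubling for contrast.
- Reference 3%, at least 5 cases: 18% at 6% (doubling), 82% at 13.5% (4.5-fold).
- Reference 1.6%, at least 3 cases: 21% at 3.2% (doubling), 71% at 7.2% (4.5-fold).

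**The case against.** The wording may be no more than shorthand. The verdict follows directly from the multi-transfused benchmark as its consequence, and Protocol 3, 5.1 and 9.1 all concern previously treated patients. I think the narrower population was probably meant. But the sentence names its own comparator, and nothing later in either document narrows it.

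A reader might go further and infer that the verdict is contradicted by the introduction, where "Estimates of inhibitor formation from retrospective and prospective clinical trials vary from as low as four percent to as high as 28 percent", since 2% lies below all of that range. The documents do not support this. The range has no time base. The 8 to 28% for severe disease is a prevalence, and the 9 to 28% trial results are from previously untreated patients. None is a two-year incidence, and nowhere does the plan use the range as a benchmark. It should not be set against 1 of 50 or fed into the binomial formula.

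The 3% is called a maximum, so it need not equal any previously treated estimate in the introduction, and it lies above all three. What remains is that it carries no citation.

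The SAP is mainly descriptive: SAP 6.4 says so, and SAP 9.1 adds no test. That limits the practical effect, but Protocol 9.2.1 lists the rule as the planned analysis of the primary endpoint. A strict trigger can also be defended as a cautious safety signal. That would justify further review of the product after one case. It would not justify stating that the incidence is higher.

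**Conclusion.** The point holds in two parts. The verdict's population is wider than the benchmark's and the trial's, which is a wording fault that is cheap to cure. The more serious part is that the one-case threshold does not support a verdict of higher even against the matched 3%. At a true rate equal to the reference, the rule returns that verdict 78% of the time for 3% and 55% for 1.6% with 50 subjects, and 70% and 37% with 80. Correcting the comparator alone would leave this in place.

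Assumptions:
- Subjects are independent and each has a full two years of risk.
- *Biannual* means per two years. If it meant twice a year, 3% per half-year is 1 − 0.97^4 = 11.5% over two years, and the one-case rule would flag a product at that rate 99.8% of the time.
- The 1.6% assumes a constant rate and covers all severities. Of its 31 cases, 29 were severe, so the rate in severe disease may be higher. A reader might want to rescale it, but the documents do not give the severe share of that cohort, so I offer no severe-only benchmark.

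**What to change.** In both Protocol 9.2.1 and SAP 4:

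1. Name the comparator as previously treated (multi-transfused) patients with severe hemophilia A and no inhibitor history, treated with other marketed Factor VIII concentrates.
2. State one two-year reference rate with its source: either the source for 3%, or the 8 per 1,000 patient-years in Protocol 1 (about 1.6% over two years), noting that it covers all severities. Replace *biannual* with per two years, if that is what is meant.
3. Remove the 2% confidence limit, which cannot be reproduced, and the one-case and 80-subject rules that follow it.
4. Conclude higher only if the exact one-sided 95% lower limit exceeds the reference: at n=50, at least 5 cases for 3% or 3 for 1.6%; at n=80, 6 or 4. Otherwise report the estimate and its upper limit descriptively.

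In SAP 9.1, add the exact confidence interval beside the reference rate.

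This needs no new data and no more subjects: one revised paragraph in each document and one more line in the inhibitor table. The cost is a claim limited to previously treated severe patients and a less sensitive verdict, with about a one in five chance of detecting a doubling at n=50. That limit belongs to the sample size, and the report should let the upper confidence limit show it.

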IDUR	Investigational drug utilization record
IRB	Institutional review board
LDH	Lactic acid dehydrogenase
PCR	Polymerase chain reaction
PEG	Polyethylene glycol
PTP	Previously-treated patients
PUP	Previously-untreated patients
SD/HT	Solvent Detergent/Heat Treated
seronegative	non-reactive in an ELISA test for antibody to the virus in question
seropositive	reactive in an ELISA test for antibody to the virus in question
SWI	sterile water for injection
USP	United States Pharmacopeia
VWF	von Willebrand Factor

Contains Confidential and Proprietary Information of Grifols Inc.

PROTOCOL SUMMARY

Protocol Number:	GBI 04-01 (formerly ATC 02-01 of Alpha Therapeutic Corporation)
Title:	A Study of Immunologic Safety for Alphanate® in Previously Treated Patients Diagnosed with Severe Hemophilia A
Study Phase:	Phase IV
Study Duration:	At least 2 years
Name of Drug:	Antihemophilic Factor (Human), Alphanate® Solvent Detergent/Heat Treated
Drug Dosage:	An appropriate dosage for the prevention and/or control of bleeding
Concurrent Control:	None
Route and Form:	Intravenous
Objectives:	To determine the immunologic and general safety of long-term use of Alphanate® in individuals with severe hemophilia A.
Subject Population:	Males diagnosed with severe hemophilia A who have been previously treated with Factor VIII concentrates, cryoprecipitate, or whole blood for a total of 150 cumulative exposure days; at least six years and not more than 65 years of age, who have no history of exposure to Alphanate® and who have never been diagnosed with antibody inhibitors to Factor VIII or to nonspecific inhibitors of coagulation.
Structure:	Multi-center study
Blinding:	Unblinded
Method of Subject Assignment:	Non-randomized
Total Sample Size:	At least fifty evaluable subjects
Pharmacokinetics:	Not Applicable
Efficacy Endpoints	Not Applicable

Contains Confidential and Proprietary Information of Grifols Inc.

Primary Endpoint	1. The incidence of Factor VIII inhibitor development.

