2.2 Treatment Comparisons

Alphanate® is the only study treatment being administered, so this is an open label, non-comparator study.

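### Two acceptance rules (no inhibitor case in 50, at most one in 80) with nothing fixing in advance which applies, so one case in the first 50 can be either a failure or a pass

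*Protocol*

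**What the plan says.** Protocol 9.2.1 starts from a benchmark: "Assuming a maximum biannual rate of inhibitor incidence of three percent in multi-transfused hemophilia patients". It then states a precision: "the 95% one-sided confidence interval for this incidence rate in a sample of 50 subjects is up to two percent". From these it draws a rule for the smaller size: "with a sample of 50 evaluable subjects monitored for two years, if one subject develops an antibody inhibitor to Factor VIII", with a titer above 0.6 modified BU/mL lasting at least a month, then "the incidence of inhibitors to Factor VIII will be judged to be higher than that for patients with hemophilia A" treated with marketed concentrates. So no case is allowed in 50.

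The next sentence gives the second rule: "If the sample size is increased to 80 subjects, no more than 1 subject may develop an antibody inhibitor to Factor VIII". SAP section 4 repeats the whole paragraph.

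The size itself is left open. Protocol 9.1 has "The sample size of 50 to 80 evaluable patients followed for at least two years". The Protocol Summary has "At least fifty evaluable subjects", and Protocol sections 4 and 8.1 also set 50 only as a minimum.

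On who can see results, SAP 2.2 says "so this is an open label, non-comparator study". Under Protocol 7.2 the sponsor's monitor confirms eligibility and assigns each subject number. Under Protocol 7.11 the sponsor's project manager is consulted before an inhibitor titer is declared unlikely to fall. SAP 10.1 rules out an interim analysis of efficacy only, and the primary endpoint is a safety endpoint.

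**The concern.** The two rules conflict over the same observation. One persistent inhibitor among the first 50 evaluable subjects is an adverse verdict if the trial is a 50-subject trial. It is acceptable if the trial becomes an 80-subject trial and no second case appears. Nothing in either document says that this choice must come before inhibitor results are known, and the sponsor both controls enrollment and can learn of cases as they arise.

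Two things are at stake. If the choice follows the result, the procedure actually carried out is neither of the two fixed rules, and its chance of clearing a product with a truly raised rate is higher than under either. And a pass at 1/80 would be open to the challenge that it was a failure at 1/50 rescued by adding subjects. The sponsor could not answer that from the documents.

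**Working it through.** **Inputs.** Benchmark 3% (Protocol 9.2.1). *Biannual* is read as per two years, which fits the two-year monitoring in the same paragraph. Rules: 0 cases in 50, at most 1 in 80 (Protocol 9.2.1, SAP section 4). Subjects are treated as independent with a common two-year probability p of a qualifying inhibitor. The sentence on 80 subjects does not repeat the titer and persistence conditions; the same case definition is assumed for both.

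**The plan's own figure.** The one-sided 95% bound of 2% at n = 50 could not be reproduced. The exact upper limit is 5.8% for 0/50 and 9.1% for 1/50. The Wald limit for 1/50 is 5.3%, and a Wald limit around 3% is 7.0%. Only the point estimate 1/50 equals 2%. This is a separate defect; nothing below uses the 2% figure.

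**Formulas.**

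- Fixed 50: P(clean) = (1−p)^50.
- Fixed 80: P(clean) = (1−p)^80 + 80p(1−p)^79.
- Stop at 0/50, extend to 80 only after exactly 1/50: P(clean) = (1−p)^50 + [50p(1−p)^49] × (1−p)^30.

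**At p = 3%.**

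- Fixed 50: 0.97^50 = 0.2181.
- Fixed 80: 0.0874 + 0.2164 = 0.3038.
- Extension: 0.2181 + 0.3372 × 0.4010 = 0.2181 + 0.1352 = 0.3533.

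**At p = 5%.**

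- Fixed 50: 0.95^50 = 0.0769.
- Fixed 80: 0.01652 + 0.06954 = 0.0861.
- Extension: 0.0769 + 0.2025 × 0.2146 = 0.0769 + 0.0435 = 0.1204.

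| True two-year rate | Fixed 50, 0 allowed | Fixed 80, at most 1 | Extend only after 1/50 | Extension minus fixed 80 |
|---|---|---|---|---|
| 2% | 36.4% | 52.3% | 56.7% | 4.4 points |
| 3% | 21.8% | 30.4% | 35.3% | 4.9 points |
| 5% | 7.7% | 8.6% | 12.0% | 3.4 points |
| 6% | 4.5% | 4.3% | 6.8% | 2.5 points |

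**Where the rise comes from.** At 3% the step from 21.8% to 35.3% is 13.5 points. Of these, 30.4 − 21.8 = 8.6 come from the more lenient rule openly stated for 80, and 35.3 − 30.4 = 4.9 from choosing after seeing the result. At 5% the split is 0.9 and 3.4 points.

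**Direction.** Extension passes every outcome that either fixed rule passes. Compared with fixed 80, it also passes the trials with no case in the first 50 that would have had two or more in the next 30, because those trials stop at 50. Its pass probability is therefore above both fixed rules at every true rate strictly between 0 and 1.

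**The case against.** The strongest reply is that 35% against 22% at a 3% rate shows no harm. The adverse verdict is that incidence is *higher* than with marketed products, and 3% is the assumed maximum for those products. A product at exactly 3% is not higher, so a clean verdict there is correct, and extension lowers the false adverse verdict from 78.2% to 64.7%. This stands. The harm lies above 3%, which is why the 5% figures carry the point.

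Second, most of the rise at 3% belongs to the published rule for 80. This also stands; fixed 80 is the fair comparison for the effect of the result-dependent choice.

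Third, a reader might infer that the sponsor intends to add subjects after a first case. The documents do not support that. The rule for 50 reads as a final verdict, and the next sentence can be read as the limit for a trial recruited to 80 from the start. The extension path is only left open.

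Fourth, a reader might infer that stated error rates are breached. The documents give no type I error, power or pass probability for the rule, so there is nothing stated to inflate.

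Finally, SAP 9.1 reports the primary endpoint as frequencies and percentages, and SAP 6.4 calls the analysis mainly descriptive. A report of 1/80 would show its case and its denominator. That limits the consequence, but SAP section 4 keeps the verdict rule, and nothing in the SAP withdraws it or fixes N.

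**Conclusion.** The concern holds in a limited form. The plan contains two acceptance rules that can give opposite verdicts on the same first case, and does not fix which applies before results are seen. This is more than a missing detail, because the primary conclusion turns on it.

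If the sponsor were to stop at 0/50 and extend only after exactly 1/50, a product with a true two-year rate of 5% would be cleared 12.0% of the time, not 7.7% or 8.6%. Over a size of 80 fixed in advance, the result-dependent choice adds 3.4 points at 5% and 4.9 at 3%. That is modest.

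These figures rest on that hypothetical strategy, on independent subjects with a common risk, and on reading the benchmark as a two-year rate. If it were a six-month rate, the two-year rate would be 1 − 0.97^4 = 11.5%, and the pass probabilities under fixed 50 and under extension would both be below 0.3%. The conflict between the rules does not depend on any of these assumptions.

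**What to change.** In Protocol 9.2.1 and SAP section 4, do one of two things:

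- State that the evaluable N (50 or 80) and its single acceptance rule are fixed before any central-laboratory inhibitor result is reviewed, and remove the other rule.
- Or write the rule as two-stage: stop and pass at 0/50; extend to 80 at 1/50 and pass only if no further case appears; fail at two or more. Report its pass probabilities at and above 3%, for example 35.3% at 3%, 12.0% at 5% and 6.8% at 6%.

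The second option does not lower the pass probability; it makes the procedure explicit so that it can be judged.

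The cost is mainly wording, and the sponsor gives up the freedom to choose N after seeing results. Fixing 50 needs no extra subjects. Fixing 80 needs 30 more than the minimum, and the two-stage rule up to 30 more, each followed for at least two years; both stay within the range Protocol 9.1 already gives.
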